Clinicaltrials.gov application number: NCT03666026

Title: *Improving Influenza Vaccination Delivery Across a Health System by the Electronic Health Records Patient Portal*

Unique Protocol ID17-001889

Submission Date: 12/14/2017

IRB Approval Date: 12/20/2017

Research Design and Methods: Describe in detail the design and methodology of the study.

SPECIFIC AIMS

The overall purpose of the RCTs is to evaluate the impact that R/R, delivered through the patient portal, could have on the flu immunization rates of UCLA Health patients. The intent is to ultimately take the information learned and create and disseminate an adaptable toolkit to other health systems.

Specific aims are

Aim #1: Adapt algorithms, educational messages, and protocols previously used for mailed or phone influenza vaccine R/R, to create a patient portal research platform. (Aim 1 is outlined in detail in IRB applications titled: Patient Portal - Patient Qualitative Interviews and Patient- Portal Provider Qualitative Interview)

Aim #2: Assess the impact of portal R/R and key design features upon flu vaccination rates and costs.

2a: Using a 4-arm RCT, clustering within practices (up to 55), compare the effectiveness of 1, 2, or 3 portal R/R's vs. 0 R/R's on influenza vaccination rates

Hyp. 2a.1 [Primary Outcome]: >1 portal R/R will increase vaccination rates vs. no R/R.

Hyp. 2a.2: More R/R messages will raise vaccination rates (3R/R > 2R/R > 1R/R > 0R/R).

OVERALL STUDY DESIGN

Subjects receiving the intervention will be patients at one of the primary care practices within UCLA Health's System (up to 55 practices), and will include patients of any age. A proportion of the patients from these practices will be selected to participate - i.e. those who meet the inclusion criteria. Randomization techniques will occur before each RCT.

Patients will either be randomized to receive 0 (control), 1, 2 or 3 flu reminder messages via the portal.

Number of Subjects

There are approx $n = 385,000$ patients in the primary care registry (RCT#1) who are active/inactive portal users and affiliated with the primary care practices of interest for this research, and will be randomized into either the control, 1, 2, or 3 reminder arms (for RCT #1).

Many patients are members of the same family. As such, the research team will assemble family units (using household address, primary telephone number, patient ID of the guarantor, and insurance member ID as the variables of commonality to create these family units). For RCT 1, for each family, 1 individual will be randomly selected as the index patient. Only index patients who are also active portal users and affiliated with a primary care practice (criteria explained below) will have their data analyzed as part of the primary analysis plan. Secondary analyses will involve all study subjects.

Gender and age: We anticipate the gender distribution to be roughly equal. All ages of patients will be included in the study; however, patient will not receive a message until they are 6 months of age, as the flu vaccine is not recommended for those less than 6 months of age.

Racial and ethnic origin: There are no enrollment restrictions based on race/ethnicity.

Inclusion criteria

A patient at one of the clinics of interest within the UCLA Health System (up to 55 practices). An individual is deemed a primary care patient of the UCLA Health System through the following algorithm:

Assigned managed care patients (UCLAMG) + Attributed patients from other payers/ACOs

- ≥ 2 PCP visits in the past 3 years; or

- ≥1 PCP visit with preventive service code in past 1 year (99381-99397 or G0438/G0439)
- All visits cannot be urgent care visits (ie excludes visits after hours or on weekends, not by urgent care codes since UCLA does not bill accordingly)

Active patient: We decided to use the algorithm outlined above and currently approved and in place by the UCLA Health System as the research team believes it to be a generalizable model that could be applied to other health systems.

Exclusion criteria

Patients will be excluded from the overall study if they are not part of UCLA's primary care registry per the above algorithm detailed in the inclusion criteria.

Creating family units

An overall address field will be constructed from the data pull including the address, city, state, and zip code fields. Primary telephone number, patient ID of the guarantor and insurance member ID will be used as other variables in the process to create the family units. The following steps taken to create these family units is described below:

1. Start with a single entry in the contact data pull
2. Add any other entries with the same patient ID as any existing entry to the family
3. Add any other entries with the same address as any existing entry to the family
4. Add any other entries with the same primary phone as any existing entry to the family
5. Add any other entries with a patient ID matching the patient ID of guarantor as any existing entry to the family
6. Add any other entries with the same insurance member ID as any existing entry to the family
7. Repeat steps 2-6 until no new matches are found - this forms a single family
8. Repeat steps 1-7 on the remaining entries to build each additional family until all entries have been associated with a family.

Please note - when there were errors with the address and telephone number, these variables were not used to group families (ex. instances with 20+ entries with the same data for telephone number).

Definition of active portal user:

We can only send portal R/R messages to patients who have signed up for the portal. Since some patients sign up for the portal but never use it, we define an active portal user as a patient (or proxy on behalf of the patient) who has used the portal within 12m (~59% of UCLA patients), and who has logged in 1 or more times in the past 12 months (reference date for login activity will be selected by the research team and then working backwards by 365 days, example of a range 8/1/17 - 7/31/18 for RCT #1 excluding their initial activation login and any subsequent logins on the same date of account activation).

Selection of index patient from each family unit

1. If the family contains any active portal user per our definition above, the index patient is randomly selected from among these patients.
2. If the family contains no active portal users, the index patient is randomly selected from all patients in the family.

Selection of the index patient for primary analysis:

1. An active portal user per the definition above
2. The patient is affiliated with one of the primary care clinics of interest
3. The patient was randomly selected as the index patient in their family unit

We will assess primary intervention effects among eligible index patients, and secondary analyses for the entire primary care registry since the impact of the intervention reflects the extent of portal penetration and high

correlation that exists among members of the same family (n=385,000 patients in RCT #1; up to 480,000 patients for RCT #2, (ISS-generated data extraction: of 430,000; IP-generated data extraction of approximately 50,000 (MRNS only)

METHODS AND STUDY PROCEDURES

The UCLA Health System is made up in part of approx 55 primary care practices. The leadership team at UCLA Health has agreed to allow these practices to participate in the 4 RCTs outlined below. Among the primary care practices (up to n= 55), patients who meet the inclusion criteria (outlined above and in section 11.1 item 4.0) will be randomized into the study arms. Below is a detailed outline of each of the four RCTs and the interventional components.

RCT - conducted 2018-19

We propose a randomized trial, where patients are randomized within practices to 0, 1, 2 or 3 R/R messages sent via the portal on a 1:1:1:1 basis. Our prior studies showed the effects of influenza R/R can vary by patient and practice factors (i.e. age, race, practice type). We will select 1 adult or 1 child per household to be the index patient for randomization since family members can affect each other's receipt of vaccine. Inclusion criteria: Outlined above.

Eligibility for R/R: Our EHR will identify subjects who are eligible for either 1 or 2 influenza vaccinations based on ACIP algorithms (2 are recommended for children <9 years who have not had a prior flu vaccination). Spacing of R/R messages: Based on our prior studies, we plan to send up to 3 R/R messages, spaced every 3-4 weeks, beginning in October; Aim 1 findings may modify plans.

Languages: R/R messages will be in English. Portal messages in Spanish will not be available during RCT 1 due to technological capabilities.

Health Literacy: We will use plain language <8th grade reading level per Flesch-Kincaid analysis. In Aim 1 we will adapt messages with input from key stakeholders (see IRB submissions titled: Patient Portal - Patient Qualitative Interviews and Patient- Portal Provider Qualitative Interview for full outline of protocol). Our message content will be rooted in decades of work by vaccine communication expertise and rooted in the Health Beliefs Model (see file named: Health Belief Model for multiple examples of the content that will be adapted for the message). The content of the R/R message will be the same for each reminder that is sent. Please see item 1.0 for the language to be used in the messages. Please note, the file titled RCT #1 Reminders is the language used in the first two reminders (sent in October and November 2018), and the file titled RCT #1 Reminders_December is the language for the third and final reminder to be sent in December 2018 for RCT #1.

Website link: the research team is working with UCLA marketing department to develop a new flu educational webpage. This webpage is currently under-development, but we will embed short health educational videos (examples below) on the UCLA website specific for this project:

<https://www.youtube.com/watch?v=EstDvA-mr5A>

<https://www.youtube.com/watch?v=QTjchoH1KYM>

The purpose of this website is to determine what subject areas of vaccine education (i.e. safety, effectiveness, general info) that patients are most interested in. All content will be approved by UCLA's marketing dept.

R/R Message Content: The content of each R/R message will be the same for each study arm. As discussed above we may modify the R/R message content slightly based the results of the prior RCTs and the qualitative interviews to follow. The number of R/R's sent will be based upon the optimal number from Aim 1 and will be identical for both study arms.

Please see item 1.0 for examples of the messages to be used (title: RCT #3 Reminders). Example message for Arm 2 same as that used in RCT #1.

Toolkit Development (Aim 3)

Toolkit and Adoption Guide: In the final year we will develop an online toolkit and adoption guide for portal-based R/R, with a manual of operations for algorithms, messages, data management protocols and costs for start-up and maintenance. Guides will contain FAQs and common scenarios, references, websites, and other materials for health systems to personalize portal R/R. We will use diffusion of innovation methods guided by our National Advisory Board. The toolkit and guide will be adaptable for pandemic flu vaccination R/R. Please note, should the language included in any of the messages outlines for RCT 1 - RCT 4 change, and amendment will be submitted.

MEASURES

After each RCT, qualitative provider and patient interviews will be conducted. Those procedures and measures are outlined in IRB submissions titled: Patient Portal - Patient Qualitative Interviews and Patient- Portal

Provider Qualitative Interview.

Independent Variables: The key variable is study group (portal R/R vs control).

Treatment Variables: Exposure to: (a) any portal R/R messages or (b) 1, 2 or 3 R/R's; see Analysis for RCT 1.

Covariates: Covariates considered for analyses (found in studies to affect flu vaccine rates) include: Practice variables will include type- (ex. pediatric, internal medicine, geriatric, or Med-Peds, and family medicine).

Patient variables will include - age (6m-17y, 18-64y, 65+y), race/ethnicity, gender, primary language (by EHR), degree of portal use, and receipt of influenza vaccination in prior years. We recognize few UCLA patients have Medicaid; we will focus on low-income groups in the dissemination phase (Aim 3).

Dependent Measures

Vaccine Outcome: The primary outcome is influenza vaccination during the vaccination season as measured by analysis of EHR data. For children <9y who had not received prior influenza vaccination, the outcome will be at least 1 influenza vaccination.

Process Outcomes: These will include: (a) total # visits to the practice during the study time period, (b) # flu vaccine or nurse visits, and (c) missed opportunities. Visits will be measured by the EHR; using ICD-10/CPT codes to classify visits to primary care as preventive, acute/chronic, or nurse-vaccination. Missed opportunities are defined as # vaccine-eligible visits during which the patient did not receive an influenza vaccination. These process metrics will help assess how the intervention worked.

Additional Measures: see file: Summary of outcome measures RCT 1 which shows additional measures, grounded in the RE-AIM framework. Found in item 1.0 of this section.

Costs: Since the intervention is implemented centrally we assume no added practice costs. We also assume practice costs/vaccination from portal R/R is identical to standard practice costs/vaccination. We will assess the time and costs of study and implementation personnel and non-personnel costs, distinguishing planning costs from intervention costs. We will measure costs using a standardized time study/resource survey sent weekly to all individuals working on the study that delineates (a) the # hours spent for each individual, and (b) research vs implementation time. We will use national salary estimates by work code from the Bureau of Labor Statistics to value personnel time in standard rates. We will measure non-personnel costs EHR hardware, software, materials.

Cost and Cost Effectiveness

Costs: We will assume that the actual per-dose vaccination costs (administration costs, vaccine costs, storage, etc.) are identical for intervention and comparison patients and equal to the average national reimbursement for an influenza vaccine dose. The difference in total costs between the study arms will be influenced by the total costs of implementing the intervention, the difference in vaccination rates within study arms, and the subsequent health care utilization by the population (which we can model from prior studies)

Effectiveness: For each RCT we will estimate effectiveness using model-based, standardized expected values (mean) at the end of each RCT. We will calculate incremental cost-effectiveness ratios (ICERs) for each intervention arm.

For example, to compare costs in RCT #1 for Arm 3 R/R's vs Arm 2 R/R's, the ICER is: $ICER (\text{Arms 3 R/R vs 2 R/R}) = (\text{costArm 3 R/R} - \text{costArm 2 R/R}) / (\text{Flu vaccine rateArm 3 R/R} - \text{Flu vaccine rateArm 2 R/R})$

In the numerator of the above equation, the costArm X is equal to [(# Flu vaccine doses given per study arm x average national vaccine reimbursement per dose) + average costs per patient in that Arm]. The denominator of the equation is the difference in model-based, standardized expected values at the end of the intervention.

STATISTICS AND ANALYTIC PLAN

Analytic Plan:

The primary outcome is receipt of influenza vaccine among eligible index patients comparing the effectiveness of 1, 2, or 3 MyChart flu reminders to zero MyChart flu reminders.

Secondary measures are receipt of influenza vaccine among all identified patients in the primary care registry (per the algorithm outlined above in the inclusion criteria), process metrics, # subsequent preventive visits, and costs.

Power Analysis:

Power was evaluated using a simulation study. We assumed a within-practice randomization plan, and expect at minimum the sample sizes reported in Table 3 (n=145,684). We further assumed, based on preliminary UCLA Health data, that influenza vaccination rates are 42% among portal users without receipt of any portal-based R/R, and 45%, 47% and 49% among users in the 1, 2, and 3 R/R arms. We estimate 1,248 portal user families per practice (we will select 1 subject per family), based on our estimated mean family size of 2.38 portal users per family, and up to 55 practices.

Adjusting for clustering of patients in practices, and assuming an intraclass correlation (ICC) of 1% (consistent with previous work), this sample size provides >90% power to detect an overall difference of 5 percentage points between portal-based R/R (combining 1, 2, + 3 R/R arms) and 0 R/R arm for all users and subgroups of interest (age and race/ethnicity). The power for the subgroups corresponds to evaluating the treatment effect within each subgroup. These power analyses represent conservative estimates based on the available patient sample—we expect larger effect sizes based upon our prior R/R studies. An estimated number of index subjects is $1,248 \times 55 = 68,640$.

Statistical Analysis- Primary Outcome

Hyp. 2a.1: Patients receiving 1, 2, or 3 portal R/R will have higher influenza vaccination rates than 0 R/R.

Primary outcomes (patient receipt of flu vaccine) are binary; our main explanatory variable will be an indicator for the receipt of any portal-based R/R.

We will employ intent-to-treat analyses using mixed effects logistic regression models with practice random effects, an approach recommended for RCTs in which the goal is to estimate the causal effects of interventions on individuals, adjusted for patient correlation within practice. In addition to the treatment variable, the covariates in the model will include patient age (6m-17y, 18-64y, 65+y), race/ethnicity, gender, primary language, degree of portal use, flu vaccination in prior year, and practice type (internal medicine, family medicine, pediatric). This method performs well in situations where the number of observations per cluster is large and for unequal cluster sizes. Hypothesis tests will be two-sided and a p value < 0.05 will be considered statistically significant. We will use SAS v9.4 (SAS Institute Inc., Cary, NC).

Hyp 2a.2: More R/R messages will incrementally increase vaccine rates (3 R/R > 2 R/R > 1 R/R > 0 R/R): As above, we will use mixed effects logistic regression models.

The major difference for these analyses is that we will test for pairwise differences between consecutive study arms. With linear contrasts we can determine if each additional R/R increases vaccination rates. Bonferroni corrections will be applied to account for multiple comparisons. The expected sample size provides >90%

power to conservatively detect an OR of 1.13 between consecutive study arms (corresponding to a 3% increase in vaccination rates from the baseline rate of 42%).

Statistical Analysis- Subgroup analysis

We will test Hyp. 2a.1 and 2a.2 stratifying by age (6m-17y, 18-64y, 65+y) and race/ethnicity (Hispanic, NH Black, NH Asian, NH White). We will apply Bonferroni corrections to account for multiple comparisons.

Statistical Analysis- Process measures

Because other process measures (# visits, # vaccination or nurse visits, and # missed opportunities) are count outcomes, we will use negative binomial mixed effects models to compare incidence rates between arms, controlling for the patient and practice covariates mentioned above.

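### As worded, the guarantor match in step 5 runs one way, so relatives linked only through a guarantor may be split into separate families depending on processing order

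*Combined protocol and SAP*

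**What the plan says.** Creating family units gives an eight-step procedure. Step 1 is "Start with a single entry in the contact data pull", with no processing order stated. Four steps then compare one field with itself: patient ID in step 2 ("Add any other entries with the same patient ID as any existing entry to the family"), address in step 3 ("Add any other entries with the same address as any existing entry to the family"), phone in step 4 ("Add any other entries with the same primary phone as any existing entry to the family") and insurance member ID in step 6 ("Add any other entries with the same insurance member ID as any existing entry to the family").

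Step 5 is built differently: "Add any other entries with a patient ID matching the patient ID of guarantor as any existing entry to the family". It sets one record's patient ID against another record's guarantor ID.

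Step 7 closes the family ("Repeat steps 2-6 until no new matches are found - this forms a single family"). Step 8 moves on: "Repeat steps 1-7 on the remaining entries to build each additional family until all entries have been associated with a family". No step merges families already finished. A note after step 8 says that address and phone were not used where they contained errors; its example is a phone value shared by 20 or more entries.

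One index patient is drawn per family. The section on the 2018-19 RCT gives the reason: relatives influence one another's vaccination. The primary model (Statistical Analysis- Primary Outcome) has practice random effects and no family term.

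**The concern.** Family grouping is the plan's only protection against relatives being randomised separately. A one-way link inside a procedure that never revisits finished families makes the result depend on where it starts. If the guarantor's record comes first, the family may close before a dependant is reached, and that dependant then starts a new family.

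Two things are at stake. First, two relatives could each become an index patient and be analysed as independent. If one is in control and the other in a reminder arm, a reminder to the second could prompt vaccination of the first. Second, the same data pull could yield different families on a rerun. That matters because the Aim 3 toolkit is to pass the algorithms on to other health systems.

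**Working it through.** **Plan's own figures.** Power Analysis gives 1,248 portal-user families per practice and 55 practices: 1,248 × 55 = 68,640 index subjects, as stated. With equal allocation, 68,640 / 4 = 17,160 are in control and 51,480 in the reminder arms. The assumed rates are 42% against (45 + 47 + 49) / 3 = 47%. Randomisation is within practice, so no clustering inflation is applied. The standard error is √(0.42 × 0.58 / 17,160 + 0.47 × 0.53 / 51,480) = 0.00436, and 0.05 / 0.00436 = 11.5. Power exceeds 99.9%, consistent with the plan's claim of more than 90%.

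**Grouping test.** Steps 1 to 8 were coded literally for one guarantor G (recorded as own guarantor) and k dependants who share no address, phone or insurance member ID. Every processing order was run.

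| k | Orders | Step 5 as written | Direction reversed | Symmetric |
|---|---|---|---|---|
| 1 | 2 | 1 family in 1, 2 families in 1 | 1 family in 1, 2 families in 1 | 1 family in 2 of 2 |
| 2 | 6 | 2 families in 4, 3 families in 2 | 1, 2 or 3 families, 2 orders each | 1 family in 6 of 6 |
| 3 | 24 | 3 families in 18, 4 families in 6 | 1, 2, 3 or 4 families, 6 orders each | 1 family in 24 of 24 |

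The case k = 2 can be followed by hand. If G comes first, neither dependant's patient ID equals G's guarantor ID, so G closes alone and each dependant then closes alone: three families. If a dependant comes first, it pulls in G, but nothing pulls in the other dependant: two families. One family never results. It also follows from the text that two dependants of a guarantor who is not in the data pull are never linked by step 5.

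When the same records share an address, every version gives one family in every order.

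**Chance of discordant arms.** Assume that two relatives are both index patients and are allocated independently 1:1:1:1. Then P(different arms) = 1 − 4 × (1/4)² = 0.75, and P(one control, one reminder) = 2 × 0.25 × 0.75 = 0.375.

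**Size, by assumption only.** The documents give neither the share f of index patients with a split relative who is also an index patient, nor the fraction c of the effect that spills over. A control patient's relative is in a reminder arm with probability 0.75, so the rise in the control rate is f × 0.75 × c × 5 points.
- f = 1% (686 patients), c = 50%: 0.01 × 0.75 × 0.5 × 5 = 0.02 points.
- f = 10% (6,864 patients), c = 100%: 0.10 × 0.75 × 1 × 5 = 0.38 points.

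At the upper end, with the reminder rate unchanged, the difference is 5 − 0.375 = 4.625 points, about 10.6 standard errors. Power stays above 99%.

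**The case against.** The best reply is that step 5 is garbled, not wrong. Its neighbours all match a shared value, and Number of Subjects lists the guarantor's patient ID among the fields that family members have in common. On that reading, step 5 means a shared guarantor ID. Order dependence then disappears, provided guarantors are recorded as their own guarantor, and siblings with a guarantor outside the data are linked too. This reading is plausible and probably reflects the intent. It is not what the sentence says, however, and both directional readings depend on order. A reader might infer that families were in fact split; the documents do not support that, because the code is not shown.

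The second reply is that the exposure is narrow, and this stands. Phone, insurance member ID and indirect links must fail as well as address. The note on errors covers only address and phone, so insurance member ID still links both ways. Both relatives must be active portal users affiliated with a study clinic, although portal use by a proxy counts for the patient.

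Third, people who share no address, phone or insurance ID may not be one household in the sense that motivates the design. That is fair. It rules out the stronger reading that one-per-household independence is broken across the trial.

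**Conclusion.** The point holds as a defect of wording with a minor consequence. As worded, step 5 makes the grouping depend on processing order for relatives joined by no other field, and it never unites two or more dependants linked only through one guarantor. This second result applies to the literal direction of the match; the reversed direction unites them in some orders only.

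The number of index patients affected cannot be derived from the documents and is probably small. If reminders spill over positively between relatives, the bias is towards no effect. The range of 0.02 to 0.38 points rests entirely on assumed inputs, and the 0.375 probability assumes independent allocation of the two relatives. A reader might infer that the sample size or power is in doubt; neither the 68,640 nor any power claim changes.

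**What to change.** Reword and code step 5 to add any entry whose patient ID or guarantor ID equals the patient ID or guarantor ID of any entry already in the family. Blank guarantor IDs should not count as matches. Apply to guarantor IDs the screen for implausibly common values that the plan uses for phone numbers (for example, 20 or more entries), so that the wider match does not merge unrelated people.

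The note on erroneous contact data is in the past tense, so families may already have been built. If a one-way rule was used, rerun the grouping with the symmetric rule and report, as a sensitivity check, how many index patients share a guarantor link. If the code was already symmetric, correcting the sentence is enough.

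The cost is about one line of code plus the screen, ideally before randomisation. The downside is slightly fewer and larger families, and so slightly fewer index patients.

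### The index-patient draw ignores practice affiliation, which is checked only afterwards; unless every patient in the pool is already affiliated, some eligible families drop out of the primary analysis needlessly

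*Combined protocol and SAP*

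**What the plan says.** **The draw.** Under *Selection of index patient from each family unit*, step 1 reads: "If the family contains any active portal user per our definition above, the index patient is randomly selected from among these patients". Step 2 covers families with no active user and draws from all members. Neither step mentions affiliation.

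**The later filter.** *Selection of the index patient for primary analysis* lists three conditions: active portal use, having been drawn, and "The patient is affiliated with one of the primary care clinics of interest". *Number of Subjects* gives the same order: "Only index patients who are also active portal users and affiliated with a primary care practice (criteria explained below) will have their data analyzed". No redraw is described for a drawn patient who fails the affiliation condition.

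**The opposite signal.** The opening of *Number of Subjects* describes the roughly 385,000 registry patients as people "who are active/inactive portal users and affiliated with the primary care practices of interest for this research". The first inclusion criterion for the whole study is "A patient at one of the clinics of interest within the UCLA Health System".

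**The pool.** *Creating family units* begins: "Start with a single entry in the contact data pull". Whether that extract holds only affiliated patients is not said.

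**The planning count.** *Power Analysis* states: "We estimate 1,248 portal user families per practice (we will select 1 subject per family". With 55 practices this becomes 68,640 index subjects.

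**The concern.** Two patient characteristics decide entry to the primary analysis: active portal use and affiliation. The draw gives priority to the first but not the second, and no reason is given. Suppose a family has one affiliated and one unaffiliated active user. Half the time the unaffiliated member is drawn, and the family contributes nobody although an eligible member was available.

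At stake is sample size in the primary analysis, and the share of mixed-affiliation families in it. The comparison between arms is not at stake: the loss depends on characteristics fixed before randomization and on a random draw, so it falls equally on all four arms.

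**Working it through.** **1. Does the loss exist?** The sections point both ways.

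- *For an affiliated-only pool:* the description of the 385,000 and the first inclusion criterion. On this reading the affiliation criterion restates eligibility and removes nobody.
- *For a wider pool:* affiliation appears twice as a further restriction on drawn patients. The registry algorithm under *Inclusion criteria* defines primary care patients of the health system by assignment, attribution and visits, without naming a practice. *Exclusion criteria* removes only people outside the registry.

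The documents do not settle this.

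**2. Loss per mixed family.** With a affiliated and u unaffiliated active users, P(family lost) = u/(a+u).

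- a=1, u=1: 1/2 = 50%
- a=2, u=1: 1/3 = 33%
- a=1, u=2: 2/3 = 67%

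**3. Loss overall.** The share q of active users who are unaffiliated is not in the documents. I assume that affiliation is independent within families and that the number of active users per family is 1+Poisson(1.38), which matches the stated mean of 2.38. Then:

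- P(family has an eligible member) = 1 − q·exp(−1.38(1−q))
- P(draw falls on an eligible member) = 1 − q
- Share of eligible families lost = 1 − (1−q)/[1 − q·exp(−1.38(1−q))]

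| q (assumed) | P(eligible member) | Lost | On a base of 68,640 | Standard error × 1/√(1−loss) |
|---|---|---|---|---|
| 0 | 1 | 0 | 0 | 1.000 |
| 2% | 0.9948 | 1.5% | about 1,000 | 1.008 |
| 5% | 0.9865 | 3.7% | about 2,500 | 1.019 |
| 10% | 0.9711 | 7.3% | about 5,000 | 1.039 |

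The patient counts are for scale only. They treat 68,640 as the number of families with an eligible member, which the documents do not establish. If affiliation runs in families, the losses are smaller.

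**4. The plan's own figures.** 1,248 × 55 = 68,640, as stated, or 17,160 per arm. Randomization is within practice, so the 1% ICC does not inflate the variance of the arm comparison. The power below uses the normal approximation for two proportions, two-sided.

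- *Primary contrast, 42% vs 47%* (47% is the mean of 45, 47 and 49), 3:1, alpha 0.05. SE = √(0.42·0.58/17,160 + 0.47·0.53/51,480) = 0.00436; 0.05/0.00436 = 11.5; power is above 99.9%. This agrees with the stated >90%.
- *42% vs 45%.* OR = (0.45/0.55)/(0.42/0.58) = 1.13, as stated. At alpha 0.05/3 = 0.0167 (Bonferroni for three contrasts), power is 99.9%, also in agreement.

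**5. Power after a loss.**

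| Loss | Primary, 42 vs 47 | 42 vs 45 (OR 1.13) | 45 vs 47 |
|---|---|---|---|
| 0 | >99.9% | 99.9% | 90.7% |
| 5% | >99.9% | 99.9% | 89% |
| 10% | >99.9% | 99.8% | 87% |
| 20% | >99.9% | 99.6% | 82% |
| 50% | >99.9% | 94.2% | 59% |

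The 47-to-49 step behaves like the 45-to-47 step (90.6% with no loss). Only these 2-point steps are sensitive, and the plan claims >90% for OR 1.13 alone.

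Subgroup power cannot be checked, because the simulation and Table 3 are not shown.

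**The case against.** **The population is already affiliated.** This is the strongest point. Besides the two statements above, *RCT - conducted 2018-19* randomizes within practices, and the primary model uses practice random effects. Neither has a defined practice for an unaffiliated index patient, which suggests that none was expected. This stands as a reason not to say that families are lost. It does not remove the inconsistency, because the affiliation filter then does nothing and the source of the families remains undefined.

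**The planning count.** A reader might infer that the primary analysis must fall below 1,248 per practice, or 68,640 in total. The documents do not support that. The 1,248 is an estimate of portal-user families counted per practice, so those families may already be tied to a practice. Nothing shows that it includes families that would later drop out.

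**Power.** A reader might also infer that the trial becomes underpowered. It does not: section 5 of the working shows both checkable claims holding even at 50% loss.

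**Representation.** Mixed families are under-represented only when counted as families. Under the present rule an active user in a k-user family is drawn with probability 1/k whatever the relatives' affiliation, so an affiliated member of a mixed pair has the same chance as a member of a fully affiliated pair. The change would raise the former to certainty. This point stands, and the case for the change therefore rests on the recovered sample size. It also fits the plan's own aim of one subject per family.

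**Scope.** The loss concerns the primary analysis only, since secondary analyses use all study subjects.

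**Conclusion.** The point holds conditionally. As written, the draw ignores affiliation, the filter comes afterwards, and no redraw is provided. Whether this costs anything depends on whether unaffiliated active users are in the pool, and on that the protocol contradicts itself.

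- If none are in the pool, the loss is zero and the affiliation criterion is redundant.
- If some are, the loss is 1.5% to 7.3% of eligible families for q from 2% to 10%. This rests on an assumed q, independent affiliation within families and an assumed family-size distribution with the stated mean.

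There is no between-arm bias and no threat to the stated power for the primary contrast or for OR 1.13. What remains is a small avoidable loss of precision (standard errors up to about 4% wider at q = 10%). It matters mainly for the assumed 2-point steps between consecutive arms and possibly for the age and race/ethnicity subgroups. The change is worth making because it is nearly free, not because the loss is shown to be large.

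**What to change.** 1. Change step 1 so that the index patient is drawn at random from the family's active portal users who are also affiliated with a clinic of interest. Use step 2 only for families with no such member; those families contribute nobody to the primary analysis under either rule.
2. State whether the contact data pull used to build families is limited to affiliated patients, and bring *Number of Subjects*, *Inclusion criteria* and the two index-patient lists into line with that statement.

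The three primary-analysis criteria stay as they are. The cost is one reworded step, one clarifying sentence and one extra condition in the selection code before randomization, using data already needed for the affiliation criterion. No patients or procedures are added. If everyone in the pool is affiliated, the change alters nothing; if not, every family with an eligible member contributes one.
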